Next, the primary study outcome of weeks worked during the baseline period (6 months preceding baseline) and the 6 months study period will be compared using dependent groups (paired samples) t-tests. Significance values for t-tests will be set at $p < .05$. The secondary work outcome, attainment of steady competitive work will be characterized using percentage of total participants achieving this benchmark. Because secondary outcomes are exploratory, these will be characterized using descriptive statistics, such as means and standard deviations.

Missing Data:

To address the issue of missing follow-up data, participants' baseline characteristics will be compared between those with and without missing data. We will also fit a logistic regression model to compare intervention and control participants with missing outcome data to determine whether missing data is completely at random. If not random, we will perform the analysis with complete cases, using LOCF imputation method. Multiple imputation techniques will be used to evaluate the robustness of our analysis for the main outcome.

References

- Albert, K.A., & Luzzo, D.A. (1999). The Role of Perceived Barriers in Career Development: A Social Cognitive Perspective. *Journal of Counseling & Development, 77*, 431-436.
- Americans with Disabilities Act of 1990, Pub. L. No. 101-336, § 2, 104 Stat. 328 (1991).
- Anthony, W.A. (1993). Recovery from mental illness: The guiding vision of the mental health service system in the 1990s. *Psychosoc Rehabil J, 16*(4), 11-23.
- Arns, P. G., & Linney, J. A. (1993). Work, self, and life satisfaction for persons with severe and persistent mental disorders. *Psychosocial Rehabilitation Journal, 17*(2), 63-79.
- Attkisson, C. C., & Zwick, R. (1982). The client satisfaction questionnaire. Psychometric properties and correlations with service utilization and psychotherapy outcome. *Eval Program Plann, 5*(3), 233-237.

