Participants will be recruited from the SE program at the Roudebush VA Medical Center. Eligible participants will be approached by their SE vocational specialist who will inform them of the study; if veterans express interest in participating, they will be provided with a study information sheet further explaining details of the study and a member of the study team will call them to schedule a time for the baseline assessment; during this time, written informed consent will be obtained.

Baseline and follow-up assessments (post-intervention and 6 month follow-up) will be conducted by trained study personnel. Currently, several research assistants in our VAMC research service have been trained in interviewing veterans with mental

illness including completing standardized symptom and psychosocial rating scales. The assessments will take approximately 60-90 minutes and participants will be paid \$30 for each of the three assessments. Next, participants will be assigned to an CBT_w group. Once a cohort of eight veterans has been enrolled, we will begin a new CBT_w group.

CBT_w groups will occur weekly for 12 weeks and last for a duration of 60 minutes per session, taking place in one of two RVAMC locations. Participants will be provided with the CBT_w participant manual containing materials pertaining to each of the 12 modules. Each CBT_w group session will be conducted by two facilitators, [name] (PI), a licensed clinical psychologist with extensive clinical and research expertise in CBT or the project manager, who has years of experience facilitating CBT interventions for veterans with mental illness (including the preliminary study of the adaptation of the CBT_w program) along with a pre-doctoral clinical psychology practicum students. Student facilitators will first be trained in the CBT_w program by [name]. Lastly, periodic fidelity assessments will be conducted by a senior investigator and trained research staff to assess adherence to the general CBT model.

Study Measures:

Unless otherwise specified, study measures will be collected baseline and the 12-week follow up point (post intervention). Some measures will be assessed at the 6 month follow up; these are exploratory.

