The possible risks to participants associated with participation of this study are a remote risk of loss of confidentiality and psychological risks. We will keep all research records private to the extent of the law. Original copies of assessment materials and digitally recorded CBT_w sessions will be kept in a locked file cabinet and on a secure server. The data will be maintained in a secured computer database in a password-protected computer, located in a limited access, locked room. Access to all data will be restricted to members of the evaluation team. Data will be kept for seven years according to state and federal regulations and destroyed at the end of that period. The other possible risk may be psychological risks associated with participation in the CBT_w group. We will try to minimize this potential psychological risk by informing subjects the CBT program and assessments are strictly voluntary and that they may drop out or quit at any time without any consequences. Participants may also skip or refuse to answer any questions that they would like.

Given the low anticipated risk of adverse events, special safety-monitoring procedures above and beyond those of the VA will be minimal. Participants will have access to the principal investigator's e-mail address and phone number and will be invited to inform the principal investigator of any concerns. All adverse events will be reported to the principal investigator who will be responsible for reporting them to IUPUI's IRB. Given that the pilot study proposed does not involve the use of experimental drugs or devices, reporting will be limited to the IRB and will not include the NIH OBA or the FDA. All procedures for safety monitoring required by the IRB will be observed.

Statistical Analysis Plan

Data will be analyzed using the Statistical Package for the Social Sciences (SPSS), version 24. First, frequency distributions and histograms will be generated to determine the normality of the sampling distribution and inspect for outliers. If the distribution is skewed, data transformations and the use of nonparametric tests in primary analyses will be considered. Secondly, descriptive statistics will be generated to characterize the demographic and background composition of the sample and levels of outcome variables at baseline and post-treatment (12 week follow up). This mean and standard deviation information obtained will be used for sample size calculation for a future expanded randomized trial.

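### No active or scheduled adverse-event ascertainment is described, so a low adverse-event count would be weak evidence that the CBT_w group is safe

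*Combined protocol and SAP*

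**What the plan says.** All of this is in the combined protocol and SAP.

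- **Risk.** Privacy/Confidentiality Issues states: "The other possible risk may be psychological risks associated with participation in the CBT_w group". It offers voluntariness as the way to reduce that risk: participants are told that "they may drop out or quit at any time without any consequences", and they may decline questions.
- **Capture.** The same section says that "special safety-monitoring procedures above and beyond those of the VA will be minimal" and that participants, who are given the principal investigator's e-mail address and phone number, "will be invited to inform the principal investigator of any concerns".
- **Reporting line.** "All adverse events will be reported to the principal investigator who will be responsible for reporting them to" the IRB. The section adds: "All procedures for safety monitoring required by the IRB will be observed".
- **Who runs the group.** Under Procedures, "Each CBT_w group session will be conducted by two facilitators": the principal investigator or the project manager, together with a practicum student.
- **Who assesses.** "Baseline and follow-up assessments (post-intervention and 6 month follow-up) will be conducted by trained study personnel".
- **What is measured.** Study Measures includes the PANSS, BDI-II and BAI. The default schedule is baseline and week 12; some measures, not named, recur at 6 months as exploratory.
- **What is analysed.** The Statistical Analysis Plan summarises secondary outcomes by means and standard deviations and contains no adverse-event summary. Missing Data compares participants with and without missing data on baseline characteristics.

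**The concern.** The plan names a risk and a line for passing events upward, but does not say who looks for events, when, or with what question. The one route it spells out depends on a distressed veteran choosing to contact the principal investigator, who may be co-leading that veteran's group. Some participants will be reluctant to do that. A veteran who stops attending, says nothing and misses the week-12 assessment could leave no trace of harm in the study data.

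At stake is the meaning of any adverse-event count later reported from this pilot. With spontaneous reporting, few or no events may mean that the group is well tolerated, or that nobody asked. The data collected under the plan could not separate the two.

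**Working it through.** There is no figure in the plan to reproduce: it states no sample size, adverse-event rate or adverse-event analysis. The check has two parts.

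**1. Could the other routes fill the gap?**

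- *Symptom scales.* By default they are taken at baseline and week 12, with nothing in between. The BDI-II looks back two weeks and the BAI one week, so distress earlier in the 12-week course that has since eased falls outside both windows. A veteran who misses week 12 has no post-intervention score. If the last-observation-carried-forward method named under Missing Data were applied to these scales, that veteran's baseline score would be carried forward and read as no change. Group means and standard deviations do not show individual worsening, and no worsening criterion is given.
- *Facilitators.* They see attenders weekly, but no section asks them to ask about, log or report distress, or to contact someone who stops attending. The fidelity checks concern adherence to the CBT model.
- *VA and IRB procedures.* They apply, but their content is not in the documents.
- *Leavers.* No recording of reasons is described. A comparison on baseline characteristics cannot show that someone left because of the group.

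**2. How much does incomplete capture matter?**

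Let N be the number of participants, p the true proportion with group-related distress, and c the share of those cases that is recorded. Treating participants as independent,

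P(no case recorded) = (1 − p·c)^N.

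Only the cohort size of 8 comes from the documents (Procedures). Assumed: p = 0.10; c = 1, 0.5 or 0.2; N = 8 (one cohort), 24 (three cohorts) or 40 (five cohorts).

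| N | c = 1 | c = 0.5 | c = 0.2 |
|---|---|---|---|
| 8 | 0.90^8 = 0.43 | 0.95^8 = 0.66 | 0.98^8 = 0.85 |
| 24 | 0.90^24 = 0.080 | 0.95^24 = 0.292 | 0.98^24 = 0.616 |
| 40 | 0.90^40 = 0.015 | 0.95^40 = 0.129 | 0.98^40 = 0.446 |

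The same point in the other direction: with zero recorded events, the exact one-sided 95% upper bound on the recorded rate is 1 − 0.05^(1/N). For N = 24 this is 0.117. Dividing by c gives the bound on the true rate: 11.7% if every case is recorded, but 0.117/0.5 = 23.5% (unrounded inputs) if half are.

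**The case against.** The strongest reply is that harm has several ways to surface. The line on reporting all adverse events is not limited to what participants volunteer. Two facilitators, one of them the principal investigator or an experienced project manager, are present each week, and sessions are digitally recorded. Trained personnel interview participants at week 12 with three symptom instruments. VA procedures and whatever the IRB requires also apply. For a talking-therapy pilot with low anticipated risk and no planned safety inference, that may look enough.

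Much of this stands, and it rules out several stronger readings:

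- *That participant contact is the only way harm can be detected.* It is the only route described for surfacing harm, which is narrower. The other routes exist but are not tied to adverse-event recording.
- *That a complaint must go to the person running the group.* The project manager may lead instead, and contact and consent pages are not in the text reviewed, so another contact may be named there.
- *That the interviews contain no adverse-event question.* The interview forms are not shown; the most that can be said is that none is described.
- *That quitting is the only safeguard, or that leaving the group means leaving the assessments.* Participants may also decline questions, and the text names the programme and the assessments separately. Nothing says that group leavers lose follow-up, and supported employment records may supply employment outcomes.
- *That a low count will be carried into the future randomised trial.* The plan carries forward means and standard deviations for sample size, and plans no adverse-event count.

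It is also fair to say that asking everyone would not give full capture, because some affected veterans will miss the interview. If a quarter of cases were missed that way, the N = 24 figure would be (1 − 0.10 × 0.75)^24 = 0.154, not 0.080. That is still well below 0.292 or 0.616.

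**Conclusion.** The point holds in this form: the plan describes no active or scheduled adverse-event ascertainment, the one capture route it sets out is passive and runs to someone who may lead the group, and neither the symptom scales nor departures from the group are linked to adverse-event recording. Followed as written, it is likely to under-record harm, and a low count would be weak evidence of safety.

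The size is illustrative. At an assumed N of 24 and true rate of 10%, the chance of recording no case rises from 8% with full capture to 29% with half and 62% with one fifth; at 40 it rises from 1.5% to 13% and 45%. Sample size, rate and capture shares are all assumptions. The qualitative conclusion needs only a small sample and incomplete capture. The change is worth making because it is cheap; the primary comparison of weeks worked does not depend on it.

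**What to change.** 1. At the existing 12-week and 6-month interviews, have a trained assessor who does not lead the participant's group ask every participant one standard open question about adverse experiences since the previous assessment. Log the answers as adverse events under the existing reporting line.
2. Name a second contact for concerns: an existing senior investigator who does not lead groups. The one who carries out fidelity assessments would serve if that condition is met.
3. Record leaving the group separately from leaving the assessments, with the reason for each, and state that group leavers are invited to both follow-ups.
4. Add a short descriptive summary to the Statistical Analysis Plan: the adverse-event count, the number who left because of distress, and the number not assessed at each time point.

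The cost is protocol wording, a few minutes within interviews already planned at 60 to 90 minutes, and a possibly higher adverse-event count. No new staff or visits are needed and the intervention does not change.

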The VA is addressing this need by implementing supported employment (SE), a psychiatric rehabilitation approach that provides individual vocational assistance to veterans with mental illness. While the SE model is empirically validated and SE programs have been shown to achieve partial success in improving employment outcomes, a sizable proportion of individuals, 40% or more, remain unemployed (Bond et al., 2008). A further challenge is job retention; veterans with mental illness who obtain jobs frequently struggle to maintain them long-term. Even in the context of high quality, evidence-based vocational services, most studies show only modest job retention of a few months (Bond et al., 2008), and consequently, frequent job losses and inconsistent vocational functioning remain a substantial and unsolved problem.

Background

Cognitive behavior therapy (CBT) is an empirically validated, recovery based intervention that has been recommended as a best practice in the treatment of mental illness (Michon, van Weeghel, Kroon, & Schene, 2005). CBT is a standard component of veteran healthcare in the VA—as an integral part of routine outpatient multidisciplinary mental health care effectively treating conditions such as anxiety, depression, and PTSD. CBT is also a central part of Psychosocial Rehabilitation and Recovery Center (PRRC) programming and a core therapeutic technique used in Illness Management and Recovery (Gingerich & Mueser, 2005), an effective and widely implemented severe mental illness self-management program. Furthermore, research indicates that CBT is well accepted by people with mental illness (e.g., Kingdon & Turkington, 1991) and is well suited to meet the treatment needs of diverse patients, including various ethnic groups (Horell & Voss, 2008), a range of diagnostic groups (Butler et al., 2006), inpatients and outpatients (e.g., Drury et al., 1996), and varying illness phases (e.g., acute versus stable; Tarrier et al., 2004).

The majority of psychiatric treatments available to veterans—both

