Rationale: Cognitive behavioral therapy (CBT) effectively reduces symptoms across a range of psychiatric conditions (Butler et al., 2006; Wykes et al., 2008); however, its benefit to functioning remains less well understood. Some studies have evidenced a positive influence of CBT on functional outcomes, whereas others have not. One possible explanation for these inconsistencies across studies is that CBT interventions are most often focused on symptoms rather than community functioning. The few CBT interventions that have been specifically designed to address functioning have shown promising results. One functional area of critical importance is work—a central goal of most veterans with (and without) mental illness. However, work functioning has received little empirical attention in the CBT domain. Despite research evidence suggesting that maladaptive thoughts about oneself and expectations about the ability to work interfere with work success (e.g., Hoffman et al., 2000; Kukla, Bonfils & Salyers, 2015; Kukla, McGuire, & Salyers, 2015), no CBT programs have been developed specifically targeting vocational themes with the goal of improving competitive work outcomes. Further, a recent paper outlined needed avenues of future study in the SE domain; Drake and Bond (2011) state that cognitive strategies may be a fruitful area to develop to help “nonresponder” consumers with mental illness who struggle with vocational dysfunction despite high quality vocational assistance. The goal of the current project is to address this gap and the serious problem of unemployment in veterans with mental illness by pilot testing the CBT for work success program (CBT_w) and assessing key employment outcomes before and after the intervention.

Overall Design:

Adult participants will take part in the 12 week CBT_w program. All participants will receive standard SE services during the study. The longitudinal design will consist of assessments of competitive employment outcomes, important psychosocial outcomes, and background and demographic variables at baseline and at two follow-up periods—immediately following the conclusion of the CBT_w program (12 week follow up point) and at a 6 month follow up. The 6 month follow up period is exploratory.

Setting and Participants:

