Inclusion criteria is a diagnosis of any mental disorder as confirmed through medical record review; common diagnoses include schizophrenia, bipolar disorder, PTSD, personality disorders, anxiety disorders, and depressive disorders. Second, participants must be enrolled in VA supported employment services. Third, participants must also have an active goal of working in the community; participants can be currently working in the community or unemployed and searching for work. Both veterans seeking employment and those currently employed will be eligible for the pilot study in order to enhance the external validity of our findings. That is, people with mental illness commonly move in and out of job search and job maintenance phases over time and our findings will apply to the average veteran receiving SE services. In addition, including veterans in steady employment as well as those who are searching for a job (and may be experiencing more vocational instability) will reduce selection bias. In other words, we are not limiting our sample to only those veterans who are highest functioning with the greatest work ability.

Exclusion criteria is a major cognitive deficit or severe medical condition that would prevent participation in the intervention and/or community work.

Intervention:

The CBT_w program includes 12 sessions that are delivered in a weekly one-hour group format. Sessions focused on identifying and modifying maladaptive thoughts related to work, enhancing self efficacy and beliefs in one's ability to succeed at work, identifying and addressing personal barriers to work, and increasing beneficial coping strategies that can be applied across employment settings, including during the job search phase and working on the job. The intervention is tailored toward both employed and unemployed persons seeking community work. Session content includes the following modules: Introduction—Work goals and work story; CBT model and work; Thinking about work; Barriers to work; Coping with stress and anxiety; Coping with anger and difficult emotions; Communication at work; Dealing effectively with people at work; Managing work success; Personal work success plan.

Procedures:

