Background Characteristics. Collected at baseline only, participant background characteristics will include sex, age, ethnicity, mental health diagnosis, educational attainment, marital status, residential status, current work status (employed/unemployed), work history (i.e., weeks worked during the six months preceding the study), residential status, and legal history (i.e., number of felony convictions). We will collect this data through a combination of SE records, patient medical records (i.e., CPRS), and participant self-report.

Competitive Employment Outcomes. Competitive employment outcomes will be assessed at baseline and the follow up periods through participant self-report and supported employment records when available. These outcomes are standard in studies of employment in persons with mental illness and will include change in competitive employment defined as change in number of weeks worked in competitive jobs, comparing the baseline period (i.e. 6 months preceding baseline) and the 6 month follow up point. In addition, achievement of steady competitive employment will be assessed at the 6 month follow up point, defined as working at least 50% of the follow up period in a competitive job.

Work-related self-efficacy. Work related self-efficacy is defined as one's perceived ability and confidence to perform work activities. Given that the adapted CBT program will seek to improve these perceptions, we will measure this construct using the Work-Related Self-efficacy Scale (Waghorn et al., 2005). The 37-item self-report scale yields a total score on a 100-point scale, in which higher scores indicate stronger work related self-efficacy. Studies suggest that the scale has adequate to good reliability and validity in adults with mental illness living in the community (Harris et al., 2010).

Motivation to work: Motivation to work will be measured by the 18-item Work Extrinsic and Intrinsic Motivation Scale (WEIMS) based on self determination theory. The WEIMS is scored on a 1 to 7 Likert scale ('Does not correspond at all' to 'Corresponds exactly') with higher scores indicating higher levels of each domain of

motivation. The WEIMS has been shown to have strong predictive validity, correlating highly with work behaviors (e.g., Tremblay et al., 2009).

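### CBT_w is given in groups of about eight, but the only outcome test treats group members as independent and nothing in the SAP addresses this

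*Combined protocol and SAP*

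**What the plan says.** The Intervention section states that the 12 sessions are "delivered in a weekly one-hour group format". Under Procedures, "Once a cohort of eight veterans has been enrolled, we will begin a new CBT_w group". The same section has each session led by two facilitators (the principal investigator or the project manager, with a student) at one of two locations.

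The Statistical Analysis Plan has one significance test of an outcome: weeks worked in two six-month periods "will be compared using dependent groups (paired samples) t-tests", with significance set at p < .05. The word groups in that sentence refers to the two paired sets of measurements, not to therapy groups. Steady competitive work is reported as a percentage and the secondary outcomes descriptively, so neither is tested.

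Two robustness steps are planned. For skew, "data transformations and the use of nonparametric tests in primary analyses will be considered". For missing outcomes, the Missing Data section names LOCF and multiple imputation. Neither uses CBT_w group, and no section mentions group effects, an ICC or an independence assumption.

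**The concern.** Veterans in one cohort share 12 weeks of sessions, facilitators, a location and a calendar period, and so much the same local job market during follow-up. If these make their changes in weeks worked alike, the veterans carry less information than their number suggests. The paired t-test would then use too small a standard error and reject too often. The usual paired nonparametric tests also assume independent pairs, so the skew fallback would not help.

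At stake is the study's single inferential statement, in a trial whose title calls it an efficacy study. As the plan stands, a reader would have only an interval or p-value that relies on independence between group members, and would not be told so.

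**Working it through.** **Inputs from the documents.** Group size m = 8 (Procedures); paired t-test at 0.05 (Statistical Analysis Plan). Sidedness is not stated; I take it as two-sided. The plan gives no sample size, power or interval, so there is no figure of its own to reproduce.

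**Assumptions.** ICC of the change score 0 to 0.10; 2 to 8 full groups of eight (N = 16 to 64).

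**Step 1: size of the effect.** Design effect = 1 + (m − 1) × ICC = 1 + 7 × ICC. Actual two-sided type I error ≈ 2 × [1 − Φ(1.96 / √design effect)].

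| ICC | Design effect | √ (factor on SE) | Type I error, formula | Type I error, simulation |
|---|---|---|---|---|
| 0 | 1.00 | 1.00 | 5.0% | about 5% |
| 0.01 | 1.07 | 1.03 | 5.8% | about 5.8% |
| 0.02 | 1.14 | 1.07 | 6.6% | about 6.5% |
| 0.05 | 1.35 | 1.16 | 9.2% | about 9% |
| 0.10 | 1.70 | 1.30 | 13.3% | about 13% |

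Worked row: at ICC 0.05, 1.96 / √1.35 = 1.69, and 2 × [1 − Φ(1.69)] ≈ 0.09. The simulation draws a normal change score as group effect plus individual error, with no true change. Results barely depend on the number of groups, and data bounded at 0 to 26 weeks give about the same figures. The signed-rank test gives 6.5–6.7%, 8.7–8.9% and 12.7–12.8% at ICC 0.02, 0.05 and 0.10. With 25% random dropout and 6 groups, the planned test gives 6.2%, 8.1% and 11.0%.

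**Step 2: a group-level analysis.** A t-test on group mean changes, with groups − 1 degrees of freedom, rejects in about 5% of null trials at every ICC and number of groups examined.

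**Step 3: what it costs when there is no clustering (ICC 0).**

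| Groups of 8 | Mean CI width relative to planned CI | Includes zero among significant primary results, true change 0.5 SD |
|---|---|---|
| 8 | 1.15 | about 5% |
| 6 | 1.22 | 16% |
| 4 | 1.45 | 41% |
| 3 | 1.86 | 61% |
| 2 | 4.8 | 82% |

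**Step 4: can the interval detect clustering?** Hold the true change fixed, use 6 groups, and vary only the ICC. Among significant primary results, the group-level interval includes zero in about 52% (ICC 0) and 63% (ICC 0.05) when there is no true change. With a true 0.5 SD change the figures are 16% and 26%. The ICC moves them by about 10 points, whereas the presence of a true effect moves them by more than 35 (52 − 16 = 36; 63 − 26 = 37). An interval that includes zero is therefore weak evidence of clustering.

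**Step 5: the SD for the later trial.** With total N, the expected sample variance divided by the true variance is (N − design effect) / (N − 1). At ICC 0.05 this is (24 − 1.35)/23 = 0.985 with 3 groups and (64 − 1.35)/63 = 0.994 with 8.

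**The case against.** The strongest objection is that no problem is shown to exist in this trial. The ICC and number of groups are assumptions, and the documents give reasons to expect a low ICC. Supported employment, per the Overview of the Problem, "provides individual vocational assistance to veterans with mental illness", and Overall Design adds that "All participants will receive standard SE services during the study". The outcome is a change "comparing the baseline period (i.e. 6 months preceding baseline) and the 6 month follow up point", so half of it predates any group. The lead facilitator is one of only two people, and dropout would shrink the groups. All of this stands. It argues for a small ICC but does not establish zero.

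A second objection is that the study is a single-arm pilot. The SAP says of its descriptive statistics that "This mean and standard deviation information obtained will be used for sample size calculation for a future expanded randomized trial". A reader might infer that ignoring groups corrupts this input. It does not: the person-level SD is almost unchanged (Step 5). The mean change is also unbiased, including with unequal groups if group size is unrelated to outcome.

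A third objection is that a group-level interval could be over-read. A reader might infer that it separates true from false positives, or shows whether significance rests on independence. Step 4 does not support that: an interval that includes zero may only reflect lower power. The objection succeeds against any diagnostic use, but not against reporting the interval as one that is valid at any ICC.

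Finally, if the skew fallback is used, a t-interval on untransformed weeks may disagree with the primary test because the scale or test has changed. That also stands, and the report should say so.

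**Conclusion.** The omission is real and minor. The only outcome test assumes independence between veterans treated together, and the SAP neither says so nor offers an analysis free of that assumption. With groups of eight, type I error is about 5% at ICC 0, 6.5% at 0.02, 9% at 0.05 and 13% at 0.10. These figures rest on assumed ICCs, a two-sided test and full groups; dropout lowers them.

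A reader might go further and infer that the planned test is invalid or should be replaced. The documents do not support that. They give no ICC, the design offers reasons for a low one, and with few groups a replacement test would lose much power. The point is a cheap improvement worth considering, not a defect that undermines the study.

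**What to change.** Record CBT_w group in the analysis file and keep the planned test as primary. Pre-specify one sensitivity analysis: a t-based 95% confidence interval on group mean changes in untransformed weeks worked, with groups − 1 degrees of freedom, in the same participants as the primary analysis. In the SAP:

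- Describe it as an interval that stays valid whether or not group members are correlated, not as a test of whether significance depends on independence. It does not override the primary result.
- Report the number of groups with it, and treat it as uninformative with two or three.
- If a transformed or nonparametric primary test is used, note that disagreement may come from the change of scale or test.

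An ICC estimate need not be required. With a true ICC of 0.05 and 6 groups, its median 95% limits are −0.08 and 0.46, too wide to be of much use.

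The cost is two or three sentences and a short extra analysis; group membership is already known from running the groups. The primary test and its power do not change. The downside is the wide interval in Step 3, which can raise doubt about a real effect when there is no clustering. With unequal groups the mean of group means also differs slightly from the mean paired change (SD of the difference about 0.04 person-level SD with 6 groups and 25% dropout).
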